4.2. Accrual – Subjects

Patients 18 years of age or older at time of discharge, a resident of North Carolina, reported a telephone number in the electronic health record, and discharged from a behavioral health hospital or a behavioral health unit will be considered exposed to the intervention, whereas patients seen at locations not utilizing the VPTC program will be considered exposed to usual care. Patients who are in the intervention arm will be treated by the behavioral health care team (licensed clinicians, health coaches, a psychiatric pharmacist, and psychiatric providers). Virtual visits are conducted telephonically. Each week a list of discharged patients will be received by the behavioral health care team.

Patients included in the analysis of this study must meet the inclusion\exclusion criteria. Patients will begin accruing based on the time the location goes live according to the role out schedule. The VPTC program is available to any behavioral health patient, but the evaluation is centered on the cohort of patients meeting the inclusion criteria.

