5. OVERALL DESIGN

5.1. Variables

5.1.1. Primary Outcome Variable

The primary outcome variable is 30-day all cause non-elective acute care post discharge utilization (ED, inpatient, and observation encounters).

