5.2.2. Virtual Psychiatric Transition of Care Program

5.2.2.1. Zero Suicide Pathway

Depending on the patient's reason for admission, patients may start the VPTC program in the zero suicide pathway. Patients that meet criteria for this higher level of care will have attempted suicide. Patients are identified from the C-SSRS screening tool along with referrals from the treatment team and treating psychiatrist. Identified patients are enrolled a day or two prior to discharge and then contacted within 24 hours of discharge, to assess for suicidality and self-harm and to review safety plans and discharge instructions. Patients are contacted daily, to every few days until they no longer need the higher-level of outreach and will be transferred to the VPTC pathway. VPTC clinicians will continue to outreach with the patient for the remaining time in the VPTC program.

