5.2.2.2. VPTC Pathway

If a patient has not attempted suicide as the reason for admission, VPTC clinicians will begin outreach with the patient within the first 24-72 hours after discharge. The first outreach with the patient will be completed by a licensed clinician who will complete a brief psychosocial assessment with the patient. After the initial outreach is completed a health coach will then reach out to the patient to set a weekly schedule. The weekly outreach with the VPTC health coach will be patient centered and patient specific. These outreach will help support patients through goal setting/treatment plans, medication support, linkage and support to community resources, and safety planning. These outreach will also help patients identify any barriers they may have in attending their follow up care with their outpatient community providers. Throughout the outreach at any point and time if a patient has a question or concern about their medication the VPTC licensed practicing nurse can contact the patient to help address those needs. At each outreach patient's safety is also assessed. At any point in the outreach if a patient endorses any safety concerns that patient will be assessed by a licensed qualified clinician to identify those safety concerns and create a safety plan with the patient.

If the patient is scheduled with a VPTC psychiatric provider for a hospital follow-up appointment, an LPN (Licensed Practical Nurse) will outreach to the patient before that visit to complete the nursing intake. The patient will then have their hospital follow up visit either with their community provider, or the VPTC psychiatric provider. The VPTC psychiatric provider will review medications that the patient started on the inpatient unit or emergency department and provide any further education, adjustments, and support. The provider is able to order the medications. The VPTC program will also have support from a psychiatric provider through weekly treatment team huddles to help support patients and identify any barriers they may be facing.

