5.3. Patient Graduation from the VPTC Program

- Reached max benefit as deemed by the behavioral health care team
- Unable to connect: 4 calls attempted over 12 days
- Transition to lower level of care
 - Patients who transition to a primary care clinic
- Transition to higher level of care
 - Psychiatry/Treatment Program
 - Readmission to an Inpatient Facility
- Declined or no longer interested in services
- Death

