7.2. Statistical analysis

Distributions of baseline characteristics for locations and patients will be compared between the intervention or control periods to assess effectiveness of the randomization, and statistical or clinical differences will be adjusted in sensitivity analyses. All analyses for treatment and control periods comparisons will use an intention-to-treat approach and results will be reported used the CONSORT extension to cluster randomized trials.

The primary outcome for this study is 30-day all cause non-elective acute care utilization. Characteristics of the locations and individuals will be summarized by levels of randomization steps, locations, and individuals. The count, rates and 95% confidence intervals of 30-day non-elective acute

care utilization in the control period will be presented and compared with that in the treatment period. The primary analysis will be conducted using generalized linear mixed models with fixed effects for intervention, and intervention multiply by the time, accounting for the cluster randomized trial design with a random cluster (hospitals) or time (steps) effect. We will estimate and report the intra class correlation coefficients for all outcome measures to assess assumptions for sample size analyses and for future investigations using similar designs and outcomes. The primary analyses will follow the intention to treat principle with an additional per protocol analysis including those who actually used VPTC. The secondary analyses will include within cluster comparisons of intervention and control periods (not adjusting for any confounding effect of time), as well as comparisons of a series of (unbalanced) quasi-parallel cluster trials between those enrolled and unenrolled clusters at each intervention enrollment period. The same analyses plan will also be applied to secondary outcomes.

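### The added per-protocol analysis of VPTC users is open to self-selection and, depending on how use is defined, to early-event bias, so it can show a difference when the program has no effect

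*Combined protocol and SAP*

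**What the plan says.** Section 7.2 makes the primary analysis intention to treat and adds an "additional per protocol analysis including those who actually used VPTC". It then states: "The same analyses plan will also be applied to secondary outcomes". It does not say whether use means being referred, enrolled, reached or retained. It names no comparator for users and no start of follow-up. The one covariate adjustment compares baseline characteristics between intervention and control periods: "statistical or clinical differences will be adjusted in sensitivity analyses". Section 7.3 deals only with missing data.

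The outcome clock starts at discharge (5.1.1): "The primary outcome variable is 30-day all cause non-elective acute care post discharge utilization". When a patient becomes a user varies:

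- On the main pathway (5.2.2.2), "VPTC clinicians will begin outreach with the patient within the first 24-72 hours after discharge".
- Under 4.2, "Each week a list of discharged patients will be received by the behavioral health care team".
- On the zero suicide pathway (5.2.2.1), "Identified patients are enrolled a day or two prior to discharge".
- The synopsis allows referral before discharge for patients generally.
- Section 5.3 lists "Unable to connect: 4 calls attempted over 12 days" among the ways of leaving the program, beside declining and inpatient readmission.

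Section 7.1 expects 40% enrollment and assumes 30-day risks of 20% in the control period and 14% with VPTC. It expects 17.6% in the whole intervention arm once non-enrollees are counted.

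**The concern.** Randomization balances sites over time. It does not balance patients who accept a telephone program against those who decline or cannot be reached. In intervention periods the users are a chosen 40%. In control periods the same kind of patient cannot be identified, so the natural comparison sets users against all control-period patients. Any difference in underlying risk between users and non-users then appears as a program effect. More settled, reachable patients would make VPTC look better; higher-risk patients steered into it would make it look worse.

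A second bias depends on the missing definition. If a patient counts as a user only once reached after discharge, someone who returns to acute care first may never qualify. Users would then carry event-free days that the control group does not have.

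The stakes are interpretive. The plan expects only 2.4 points by intention to treat (20% against 17.6%) but 6 points in enrollees. The per-protocol result is the planned utilization estimate that corresponds to the 6 points, so readers are likely to lean on it.

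**Working it through.** **The plan's own figures.** The Hussey-Hughes stepped-wedge variance was used with 7 clusters, 8 periods, one cluster crossing per step, 81 per site-quarter, ICC 0.20 and total variance 0.20 × 0.80. The standard error is 1.87 points and power for 20% against 14% is 0.894 (stated: 0.89). Other variance conventions at 81 give 0.82 to 0.96. Sample size: 81 × 1.1 = 89.1; × 56 site-quarters = 4,990; × 28 intervention site-quarters = 2,495. Diluted risk: 0.4 × 0.14 + 0.6 × 0.20 = 17.6%. The inputs are therefore understood as the plan meant them.

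**Self-selection alone, no program effect.** From 7.1: overall risk 20%, uptake 40%. Assumed: user/non-user risk ratio r. User risk = 0.20r / (0.4r + 0.6).

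- r = 0.9: 0.180 / 0.96 = 18.8%, 1.3 points of apparent benefit.
- r = 0.8: 0.160 / 0.92 = 17.4%, 2.6 points of apparent benefit (OR 0.84).
- r = 1.25: 0.250 / 1.10 = 22.7%, 2.7 points of apparent harm.

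**Early events alone, no program effect.** Assumed: constant hazard, first contact on day d, and early returners becoming users at f times the usual rate. λ = −ln(0.8)/30 = 0.00744 per day, and E = 1 − exp(−λd) is the risk before day d. User risk = (fE + 0.20 − E) / (fE + 1 − E).

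| First contact | E | Spurious benefit, f = 0 | f = 0.5 | f = 1 |
|---|---|---|---|---|
| Day 1 | 0.0074 | 0.6 points (OR 0.96) | 0.3 | 0 |
| Day 3 | 0.0221 | 1.8 points (OR 0.89) | 0.9 | 0 |
| Day 7 | 0.0507 | 4.3 points (OR 0.75) | 2.1 | 0 |

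Against the 6-point assumption, f = 0 amounts to 10%, 30% and 71%, and f = 0.5 to 5%, 15% and 35%. If f = 0 but half of users enroll before discharge, the bias is 0.3, 0.9 and 2.1 points.

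**Both together (day 3, f = 0).** Observed user risk = 1 − (1 − user risk)^(27/30). With r = 0.8 it is 15.8%, or 4.2 points of apparent benefit. With r = 1.25 it is 20.7%, or 0.7 points of apparent harm (OR 1.04). The sign changes at about r = 1.17.

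**Precision of the proposed alternative.** Same variance formula on all eligible patients: 81/0.40 = 202 to 96/0.40 = 240 per site-quarter, variance at the mean of 20% and 17.6%, ICC 0.01 to 0.20 (assumed range; the plan uses 0.20). The intention-to-treat standard error is 1.06 to 1.26 points. Dividing by an uptake difference of 0.40, treated as fixed, and multiplying by 1.96 gives a 95% half-width of 5.2 to 6.2 points. Multiplying by 2.447 (an illustrative 6-df t) gives 6.5 to 7.7.

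**Cost of a landmark.** The share of 30-day events before it is E/0.20: 11% at day 3, 25% at day 7 and 43% at day 12 (E = 0.0854). Under constant hazards a true 20% against 14% becomes 1 − 0.80^(18/30) = 12.5% against 1 − 0.86^(18/30) = 8.7% after day 12, a difference of 3.9 points.

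**The case against.** The best defense is that this is one supplementary analysis beside an intention-to-treat primary, and that nearly every users-only analysis has self-selected users. Nothing in the documents says it will support a claim. That limits the importance of the point and is accepted. It does not make the result interpretable, and the analysis is prespecified for the secondary outcomes too.

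A second defense is that the planned sensitivity adjustment might absorb some measured differences if it were run on users against control-period patients. It might. But the plan does not tie it to that set, and it would reach neither unmeasured selection nor early events.

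The third defense concerns early events, and much of it stands. A reader might take the call rule in 5.3 as a 12-day window in which use is decided, and so infer up to 7.5 points of bias. The documents do not support that: the rule is an exit from the program, and enrollment may come before any successful call. A reader might also treat 10%, 30% and 71% of the assumed effect as the expected bias. Those are upper ends. The outcome includes ED and observation visits, and nothing says such a visit prevents later enrollment. The day-7 case rests on the weekly list, whereas 5.2.2.2 has outreach starting at 24 to 72 hours.

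**Conclusion.** The concern holds, limited to the supplementary analysis. As written, it can show a difference with no program effect, because it selects on patient behavior after allocation and ties no adjustment to predictors of use. Self-selection is the firm part, and its direction is unknown: about 2.6 points of benefit at a risk ratio of 0.8, and a similar amount of harm at 1.25. Early-event bias is conditional on use meaning reached after discharge. It then runs from zero to 0.6, 1.8 or 4.3 points for contact at day 1, 3 or 7.

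The sizes rest on the plan's 20% risk and 40% uptake, a control-period comparator, a constant hazard and assumed selection ratios. The documents give no event timing and no user or non-user risks. It would be wrong to infer that the analysis must favor VPTC, or that the primary result is compromised; intention to treat counts every eligible patient whether or not they enroll.

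**What to change.** As the supplementary estimate of the effect in users, report a complier-average risk difference: the period-adjusted intention-to-treat risk difference divided by the observed intervention-minus-control difference in VPTC enrollment, with a cluster-level small-sample interval. Enrollment status is already reported from HealtheCare (section 7). Check control-period enrollment there too, rather than assuming it is zero.

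The cost is mainly SAP wording. The plan presents odds ratios and states no fixed period effect, so a period-adjusted risk difference must be added. The interval is wide: with the t quantile its half-width exceeds the assumed 6-point effect. The estimate assumes that the offer acts only through enrollment, and it gives no new test beyond intention to treat.

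If a users-only comparison is kept:

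- Define use and the date on which it is established.
- Name the control-period comparator.
- Require both groups to be event-free to the same landmark day and count outcomes from there.
- Label the result descriptive, because self-selection remains.

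The landmark day is a choice to be justified; 5.3 does not supply it. The SAP should state that a landmark drops early events, discards any early program effect, and conditions on event-free status that VPTC may itself change. An earlier day loses fewer events but classes later-reached users as non-users. A landmark at day 7 or later cannot serve the 7-day office-visit outcome, where only the complier-average estimate should be used.

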4.3. Participating sites

The program has been piloted at AH Stanly as part of usual care. AH Stanly will not be included in the quantitative assessment. As part of the research design and rollout of this project, randomization will occur at the site level. CORE will randomize the facility participation order in advance of project kickoff. Site enrollment will begin with 1 facility, adding on 1 additional facility on a rolling basis in 3-month intervals, until all 7 facilities are active in using the VPTC program. Once added, sites will begin utilizing the program in their daily practice among the target patient population.

The following Atrium Health sites will be randomized for participation in this project.

- AH Kings Mountain Psychiatry
- AH BH Davidson - Fraser Fir
- AH BH Davidson - River Birch
- AH BH Charlotte - ED OBS

- AH BH Charlotte - North and South
- CMC Main 6B
- AH BH Davidson - Mountain Laurel

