5.2. Trial Design

5.2.1. Justification for stepped wedge cluster randomized control trial

The primary aim is to assess the effectiveness of a structured multidisciplinary care plan (intervention), compared with usual care (control) on 30-day all cause non-elective acute care utilization (ED visits, observation, and inpatient encounters). The VPTC program will be delivered at the level of location or cluster, thus minimizing contamination and the risk of selection bias, if subjects were randomized at the individual level. Therefore, the unit of randomization and analysis for this study will be the cluster. Considering logistical constraints and design rigor, the intervention will be rolled out sequentially instead of at the same time. Moreover, substantial and differential cluster-effects may exist because of distinct volume and characteristics of patients in each hospital. Thus, the stepped wedge design is advantageous compared with other alternative designs.

The stepped wedge design implies a baseline period, in which no clusters are exposed to the intervention. Then, at the chosen time interval of three months, one location will be randomized to cross from the control to intervention (Figure 1). This process continues until all seven locations have crossed over to the intervention. The order of this cross over process will be randomized. We will use randomization to assign location order so that if a high or low volume location is assigned cluster 1, a high or low volume location is assigned cluster 7. The single ED location will be assigned to cluster 4. SAS Enterprise Guide version 8.2 will be used for the randomization. Allocation will be communicated only to the behavioral health team initially to prevent contamination. Locations will learn of allocation in the month preceding roll-out. Patients in included locations will be blinded to the intervention or control period.

An example of the roll out schedule

Location	August 2021	November 2021	February 2022	May 2022	August 2022	November 2022	February 2023	May 2023
Location 1	0	1	1	1	1	1	1	1
Location 2	0	0	1	1	1	1	1	1
Location 3	0	0	0	1	1	1	1	1
Location 4	0	0	0	0	1	1	1	1
Location 5	0	0	0	0	0	1	1	1
Location 6	0	0	0	0	0	0	1	1
Location 7	0	0	0	0	0	0	0	1

1=Virtual Psychiatric Transition of Care Program; 0=Usual Care

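### The secondary quasi-parallel comparisons have no comparator in the last period, and in the other six, with no use of each location's baseline rate, they are dominated by chance differences between locations

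*Combined protocol and SAP*

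**What the plan says.** Section 5.2.1 describes seven locations crossing over one at a time, every three months, in randomized order. It begins from a common control quarter: "The stepped wedge design implies a baseline period, in which no clusters are exposed to the intervention". At the other end, "This process continues until all seven locations have crossed over to the intervention". Section 4.3 agrees: "adding on 1 additional facility on a rolling basis in 3-month intervals, until all 7 facilities are active". The ED location is fixed at position 4, and positions 1 and 7 are linked by volume. Section 7.5 puts last enrollment in July 2023, so the quarter starting May 2023 lies inside the study.

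Section 7.2 makes a generalized linear mixed model the primary analysis and adds two secondary ones. The first is within locations: "The secondary analyses will include within cluster comparisons of intervention and control periods (not adjusting for any confounding effect of time". The second is the subject here: "comparisons of a series of (unbalanced) quasi-parallel cluster trials between those enrolled and unenrolled clusters at each intervention enrollment period". Both carry over to the other endpoints: "The same analyses plan will also be applied to secondary outcomes".

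The plan does not say what happens when no location is unenrolled, how a one-location arm is handled, or whether the series is pooled. It also does not say whether a location's own baseline outcome rate is used. Differences in baseline characteristics are adjusted in sensitivity analyses only.

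**The concern.** A comparison at each enrollment period needs locations on both sides, and the final period has none on the control side. Where one arm is a single location, that period's data cannot separate the program from the location.

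The wider difficulty is that each contrast sets some locations against others. The protocol expects those locations to differ: "substantial and differential cluster-effects may exist because of distinct volume and characteristics of patients in each hospital". It also assumes an ICC of 0.20. Every location contributes an all-control quarter that could remove most of a stable difference, but the analysis as described does not use it. What is at stake is how the secondary results are read: six noisy figures per outcome, some of them large in either direction by chance, reported beside the primary result.

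**Working it through.** **Counts.** Enrolled v unenrolled locations, from the example schedule in section 5.2.1 (the counts follow from one location per step, whatever the dates):

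| Aug 21 | Nov 21 | Feb 22 | May 22 | Aug 22 | Nov 22 | Feb 23 | May 23 |
|---|---|---|---|---|---|---|---|
| 0 v 7 | 1 v 6 | 2 v 5 | 3 v 4 | 4 v 3 | 5 v 2 | 6 v 1 | 7 v 0 |

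**Inputs (section 7.1).** Control rate 20%, so total variance 0.20 × 0.80 = 0.16. ICC 0.20. Effect 6 points, or 2.4 points after dilution by 60% non-enrollment. Eligible patients per location-quarter are not given as an average. I take m = 96/0.40 = 240, inside the stated range of 159 to 300, and also show the planning value of 81.

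**The plan's own figure.** The standard stepped-wedge variance formula with m = 81, between-location variance 0.032 and residual 0.128/81 gives a standard error (SE) of 0.0187 and power 0.894, against the stated 0.89. So this reading of the ICC is the plan's. No figure is given for the quasi-parallel series.

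**Single-period SE, analyzed by location.** With k locations enrolled, SE = √[(τ² + σ²/m)(1/k + 1/(7−k))], where τ² = 0.20 × 0.16 = 0.032 and σ² = 0.80 × 0.16 = 0.128. At m = 240 the bracket is 0.032 + 0.000533 = 0.032533, of which 98% is location variance.

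| Periods | m = 240 | m = 81 | m = 81, ICC 0.05 | m = 81, ICC 0.01 |
|---|---|---|---|---|
| 1 v 6, 6 v 1 | 0.195 | 0.198 | 0.107 | 0.064 |
| 2 v 5, 5 v 2 | 0.151 | 0.153 | 0.083 | 0.050 |
| 3 v 4, 4 v 3 | 0.138 | 0.140 | 0.076 | 0.046 |

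The first two columns use ICC 0.20; the values 0.05 and 0.01 are assumptions to show the range. At ICC 0.20 and m = 240 the SE is 0.138/0.024 = 5.8 to 0.195/0.024 = 8.1 times the diluted effect. Two-sided normal power is about 5% for 2.4 points and 6–7% for 6 points.

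**Permutation limits.** Counting only the fixed ED position, with orders equally likely, there are 6, 15 or 20 possible allocations per period. The smallest one-sided p-values are 1/6, 1/15 and 1/20. The volume link changes the set further.

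**ED location.** If its rate differs by D from the others, its fixed position adds −D/6, −D/5, −D/4, +D/4, +D/5 and +D/6 to the six contrasts. Under weights symmetric about the middle, such as 6, 10, 12, 12, 10, 6, these sum to zero.

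**Pooling the six periods.** Take weights k(7−k)/56. The location crossing at step i then carries total coefficient (4−i)/8, with sum of squares 28/64 = 0.4375. Independent quarter-level error carries 7 × 56/56² = 0.125. Let a be the stable location variance and b the location-by-quarter variance plus σ²/m.

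- Raw pooled variance = 0.4375a + 0.125b
- Change-from-August-2021 pooled variance = (0.4375 + 0.125)b = 0.5625b

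| Case | a | b | Raw SE | Change SE |
|---|---|---|---|---|
| ICC 0.20, m = 240, stable | 0.0320 | 0.00053 | 0.119 | 0.017 |
| Same, one fifth by quarter | 0.0256 | 0.00693 | 0.110 | 0.062 |
| Same, half by quarter | 0.0160 | 0.01653 | 0.095 | 0.096 |
| ICC 0.01, m = 81, stable | 0.0016 | 0.00196 | 0.031 | 0.033 |

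Change scores help only when a exceeds b. A full stepped-wedge model with location and period effects gives 0.011 in the first case and 0.039 in the second.

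**The case against.** The analysis is secondary, and the plan itself calls it unbalanced and quasi-parallel. It complements the within-location comparison: one leaves time uncontrolled, the other holds calendar time fixed. No power is claimed for it and no period-specific test is specified. The 7 v 0 period might be thought to drop out by itself, having no unenrolled cluster. Non-use of baseline is inferred from silence. The pooled estimate resembles the primary contrast and is less precise. All of this is fair and limits the weight of the point. It does not supply the missing rules or make a single-period contrast informative.

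A reader might infer more, in three ways that the documents do not support.

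- *That the series is biased, presenting location differences as program effects.* The order is randomized, so under a fully random order a location's difference falls on either side by chance and averages to zero. A correctly clustered interval would show this as width. The systematic exception shown here is the ED location, always control in steps 1–3 and always exposed from step 4.
- *That false positives would be rife.* At m = 240 a patient-level comparison with no location effect would reject a true null about 78% of the time: 2Φ(−1.96 × √(0.000667/0.032533)), where 0.000667 = 0.16/240. But section 5.2.1 makes the cluster the unit of analysis, and section 7.2 calls these cluster trials. That figure describes an analysis the plan points away from.
- *That the main result is compromised.* The primary model is a separate analysis, and its stated power of 0.89 does not depend on this series.

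**Conclusion.** The point holds as one of imprecision and incomplete specification in a secondary analysis. One of the seven planned comparisons cannot be made, and two rest on a single location in one arm. At the plan's ICC of 0.20, the six that can be made have standard errors of 0.14 to 0.20 against an expected 0.024, and chance location differences supply nearly all of that.

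The size rests on ICC 0.20, a planning assumption that section 7.2 says will be checked. It depends little on cluster size. At an assumed ICC of 0.01 with 81 per cell, single-period standard errors are still 0.046 to 0.064, about two to three times the diluted effect, but location differences no longer dominate.

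The benefit of using baseline depends on stability. It is large if location effects are stable, moderate if one fifth of the location variance is by quarter, and absent if about half is, or if the ICC is near 0.01 with 81 per cell. Even in the best case, power for 2.4 points is about Φ(0.024/0.0173 − 1.96) = 28% by normal approximation, so the pooled result is supportive only.

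**What to change.** Amend section 7.2 as follows.

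1. Limit the series to the six quarters from November 2021 to February 2023, and state that May 2023 has no comparator.
2. Analyze at location level, adjusting each location's rate for its August 2021 rate, as a covariate or as change from baseline. Name the choice in advance, because change scores can lose precision if the ICC is low or location effects drift.
3. Report one pooled within-period estimate per outcome with stated weights. Symmetric weights such as k(7−k) cancel a constant ED difference.
4. Take the p-value and interval by re-randomizing over the orders actually permitted. Fixing the ED location leaves at most 6! = 720 orders, and the volume link between positions 1 and 7 restricts these further, so that rule must be written precisely enough to list them.
5. Show the period-specific raw differences descriptively, without tests, and flag the 1 v 6 and 6 v 1 quarters as resting on one location in an arm.

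The cost is SAP wording and a short program, with no new data. Period-specific p-values are lost, as is the purely between-location view as an inferential analysis, though the raw differences remain visible.
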